As listed in the table below, we will collect 7 data elements: (1) Veteran characteristics; (2) Intervention dose/exposure; (3) Narrative Communication measures; (4) Social Cognitive-Theory-based measures; (5) Hypertension management behaviors; (6) Blood Pressure (BP) (blood pressure will be checked by RA at in-person visits at baseline and at 6 month follow up); and (7) Implementation Data including Process Measures and measures of Fidelity. We will gather these elements through initial data collection (CDW), over-the-phone screening survey, baseline visit and follow-up visit observations and surveys, texting system and phone calls to participant.

• Table 8. Seven Key Data Elements		Timing	Source
1. Veteran Characteristics			
Participant Demographics		1	S,C
Comorbidities, VA Utilization		1	C
2. Intervention Dose/Exposure			
Number of videos watched and time spent viewing		2	S
Which was selected video?		2	S
3. Narrative Communication			
Video Transportation Scale		2	S
Homophily (personal relevance)		2	S
4. Social Cognitive Theory			
Beliefs About Medications (BMQ)		1,4	S
Self-efficacy for hypertension (e.g.: MASES-R, PEPP)		1,4	S
5. HTN management behaviors			
Avoid Salt, Be Physically Active, Monitor your BP(H-SCALE, PEMH)		1,4	S
Talk with your doctor (H-SCALE)		1,4	S
Take Your Medicines: Morisky ; and administrative data adherence (MPR)		1,3,4	S, C
6. Primary Outcome (H1)			
Measured BP (systolic/diastolic)		1,4	BP, C
7. [Implementation Data/ Process Measures/Fidelity]		3,4	RA, S, T
Text message opening (subgroup)		3	T
Responses to text assessment		3	T
Confirmation of text receipt		4	S
Phone calls for texting assistance		3	RA
Staff time spent for implementation		3	RA
Persistence/Early Discontinuation of Texting Protocol		3	T
Reasons for discontinuation		5	P

1=Baseline, 2=Immediately post-Video Viewing; P, 3=Repeated throughout 6-month study period, 4 = six-month follow-up; 5= phone call to drop-out.

Source: S = Survey; C = CDW data; RA=Research assistant; T=Texting System; P=phone call to participant; BP = Blood pressure cuff, standard protocol

Randomization

Random allocation to CTC or control will be stratified by site, and within each site, we will stratify by sex (women/men). Our statistician will create a randomization table with randomization blocks varying between 5 and 10 subjects.

Interim Data Analysis

We do not plan to conduct interim data analysis

Missing Data/Subject Dropouts

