Missingness not at random may introduce bias. Advance planning through sound data collection and quality control will be used to minimize this bias. We will use all available data regardless of whether a patient has a complete record. Group means will be reported as least-squares means, the predicted marginal mean values, or those that would be expected with a balanced design. Participants with missing data will be compared to those without. Inverse probability weight in and pattern-mixture modeling using the longitudinal data structure, for non-ignorable missing data, will be considered.

Covariates for Adjustment Models

We will look at the balance of randomization and adjust for demographics and behavioral variables if imbalanced.

Data Transformations

N/A

Analytical Sets

We intend to include all patients in intent to treat analysis.

Monitoring Adverse and Serious Events

Because this is a low-risk trial of an educational DVD, we do not expect SAE's or AE's. We will plan to report any SAE's defined as death of participant or hospitalizations reported at 6-month follow-up.

At the time of recruitment, patients experiencing hypertensive urgency, as defined by JNC as Blood Pressure Systolic \geq 180 OR Diastolic \geq 120, regardless of symptoms, will be referred to urgent care and a notification letter will be sent to their primary care physician. If a patient reports symptoms related to the hypertensive urgency, even if before viewing the intervention DVDs, this will also be reported as an AE. AE's also include stress related to watching the DVD. All AE's reported at baseline and 6-month follow-up will be recorded and submitted at Continuing Review.

Analysis Plan

We will first identify key distributional features for all variables of interest (non-normality, skewness, ceiling or floor effects, presence of implausible values, outliers, etc.) and calculate descriptive statistics. We will document recruitment and retention with a CONSORT diagram. Following best practice, baseline differences between intervention and comparison groups will be based on standardized differences, not simply tests of statistical significance. All primary hypotheses will be tested by intent-to-treat; secondary analyses will account for important covariate imbalances between groups, levels of adherence to the intervention protocol, and missing data. All analyses will be two-sided, with alpha error = 0.05.

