Hypothesis 1: (Primary Hypothesis) The difference in blood pressure from baseline to 6 months will favor CTC intervention group by 5mm Hg, compared with the change in control.

H1 postulates a difference-in-differences between study groups. We will use study group, assessment time, and group-time interactions as predictors in regression models. With this parameterization, the coefficient for the group-time interaction represents differential change for intervention vs. comparison. Multilevel mixed-effects generalized linear models will: (1) model the outcome distribution with an appropriate link function; (2) account for clustering of repeated measures within individual; (3) adjust for observed group imbalances as secondary analyses; and (4) support secondary mediation analyses as described below. The most general structure of the mixed model is $y = X\beta + Z\gamma + \epsilon$, where the y matrix is the observed outcomes, β is a vector of fixed-effect parameters with design matrix X , γ is a vector of random-effect parameters with design matrix Z , and ϵ is a random-error vector. We will assume that γ is independent of ϵ and has a multivariable normal distribution with mean $\mathbf{0}$. We will examine residuals to seek gross violations of underlying assumptions, and explore approaches to address violations such as variable transformation, outlier trimming, or placing bounds on the extent that extreme observations can affect conclusions.

Hypothesis 2: Self-efficacy and hypertension management behaviors during 6-month follow-up will be greater for those in the CTC intervention group than comparison.

As Self-efficacy and HTN management behaviors (salt intake, physical activity, doctor-patient interaction, monitor BP) will be measured as self-report at baseline and follow-up, we can measure these as differences in change ("difference-in difference") between study groups, and mirror the analysis plan for H1.

In addition to self-report, for "Take your medicines" (medication adherence) we will use administrative data to calculate refill-based measures (ie: MPR) for each HTN medication and average these over six-month periods (before and during intervention). We will again use a repeated measures analysis (like H1).

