Power is driven by our most distal outcome, Blood Pressure (H1). Our sample size calculations are performed to detect a difference in the change in BP, comparing intervention and control. We carry out the calculations to determine sample sizes that would detect significant effects at the 2-sided 0.05 level, at 80% power. Difference in BP for our video stories alone ranged up to 6mm Hg, and as low as 2.7mm Hg (adjusted difference in systolic BP in VA stories). We have designed CTC to result in a stronger effect, compared with our prior VA Stories. With this rationale in mind, we calculated power to achieve a conservative and meaningful difference of difference in BPs of 5mm Hg. We used a repeated measure power calculation to estimate the group-time interaction for the difference of differences statistical analysis. Derived from our prior work, follow-up rates, within-person correlation of repeated measures of BP and standard deviation of a single BP measurement were used for the estimates. With our recruited sample of 600 (and assuming follow-up rates, over-time within-person correlation, and BP standard deviations from our prior work (85% follow-up, correlation = 0.5, SD = 18 (equivalent to variance of 324)), we have over 80% power (alpha 0.05) to detect a difference of 5mm Hg. In fact, we calculated power for a range of scenarios, and are able to maintain the 5mm Hg detection with a lower follow-up rate of 82%.

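### The primary model leaves out the stratification factors site and sex, so its standard error is slightly too wide if mean BP change differs between strata

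*SAP*

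**What the plan says.** SAP, Randomization: "Random allocation to CTC or control will be stratified by site, and within each site, we will stratify by sex (women/men". The Protocol's Objectives (Aim 2) describe the same design.

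SAP, Analysis Plan, Hypothesis 1: "We will use study group, assessment time, and group-time interactions as predictors in regression models". The treatment effect is the group-by-time coefficient, a difference between arms in within-person change. The only clustering named is that of repeated measures within a person.

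SAP, Covariates for Adjustment Models: "We will look at the balance of randomization and adjust for demographics and behavioral variables if imbalanced". The opening of the Analysis Plan, Hypothesis 1 and the Secondary Analyses paragraph all make adjustment for imbalance a secondary analysis. Imbalance is to be judged by standardised differences, and no cut-off is given.

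Site otherwise appears in the analysis only as a secondary look at the effect by site. No section puts site or sex in the primary model.

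**The concern.** Stratified allocation removes stratum differences from the true sampling error of the arm comparison. If the model leaves the strata out, those differences remain in its residual variance. The reported standard error then exceeds the true one, the interval is too wide, and the test rejects less often than its nominal level.

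The imbalance rule does not close the gap. Stratification keeps site and sex close to balanced, so the rule will not select them, and if it did, only a secondary model would change. The secondary analysis by site leaves the primary standard error as it is.

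A little precision is at stake, and so is a model choice that should be settled before the data are seen. The Protocol's Abstract reports p = 0.06 for the earlier study's six-month result, so a borderline result is a realistic prospect. A later choice between models with and without the strata would then be awkward to defend.

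**Working it through.** **Inputs.** From the SAP, Power Calculations: 600 recruited, 85% followed up, within-person correlation 0.5, SD of one reading 18 mm Hg, target difference 5 mm Hg. From the SAP, Analysis Plan: "All analyses will be two-sided, with alpha error = 0.05". From the Protocol, Introduction: a target of 20% women, 60 per site and 120 in all, which fits 300 participants per site. Assumed: 1:1 allocation (no ratio is stated), dropout at random, and all site and sex differences below, since the documents give none.

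**1. The plan's own figure.** SD of change = 18 × √(2 × (1 − 0.5)) = 18. Followed per arm = 300 × 0.85 = 255. SE = 18 × √(2/255) = 1.594. Power = Φ(5/1.594 − 1.96) = 88.0%. At the SAP's lower follow-up of 82% there are 246 per arm, the SE is 1.623 and power is 86.9%. Both agree with the SAP's statement that "we have over 80% power (alpha 0.05) to detect a difference of 5mm Hg".

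**2. Would the imbalance rule select the strata?** Stratified allocation was simulated 4,000 times under each of three block schemes: sizes 5 or 10, any size from 5 to 10, and even sizes 6, 8 and 10. The largest standardised difference for site or sex was 0.093, and the 99th percentile was about 0.06 or less. None passed 0.1, a cut-off assumed here.

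**3. Differences in BP level.** A level gap of D between sites and E between sexes adds a = D²/4 + 0.16E² to both variances and to the covariance of the two visits (0.16 = 0.2 × 0.8). With complete data, a cancels from the variance of change and the SE does not move. With 15% of follow-up readings missing, the information per arm is 255·V⁻¹ plus 45/V₁₁ in the baseline cell, where V is the 2 × 2 covariance matrix of the two visits. This gives:
- no gap: SE 1.564;
- D = 10, E = 5: SE 1.566 (0.16% wider);
- D = 15, E = 10: SE 1.5695 against 1.5639 (0.35% wider).

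The base value is below 1.594 because the mixed model also uses the baseline readings of those lost.

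**4. Differences in BP change.** A gap in mean change of d between sites and e between sexes adds d²/4 + 0.16e² to the change variance of 324 when the strata are omitted. Reported SE = √(324 + added) × √(2/255). The true SE under stratified allocation stays at 1.594. True type I error = 2 × (1 − Φ(1.96 × reported/true)). Power = Φ((5 − 1.96 × reported)/1.594).

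| Site gap d | Sex gap e | Added variance | Reported SE | Excess | Type I error | Power |
|---|---|---|---|---|---|---|
| 0 | 0 | 0 | 1.594 | 0% | 5.0% | 0.8803 |
| 5 | 0 | 6.25 | 1.609 | 1.0% | 4.8% | 0.8765 |
| 5 | 5 | 10.25 | 1.619 | 1.6% | 4.65% | 0.8741 |
| 10 | 0 | 25 | 1.6545 | 3.8% | 4.2% | 0.8648 |
| 10 | 5 | 29 | 1.664 | 4.4% | 4.1% | 0.8623 |

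For the site gap of 10 alone, the 95% interval half-width is 3.24 instead of 3.12 mm Hg. If the SD of 18 already contains the stratum differences, adding the strata would cut the SE by 1.0% (d = 5) or 3.9% (d = 10).

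**5. Check with the planned type of model.** Random-intercept mixed models were fitted to simulated stratified trials, 60 per scenario. The table shows the mean SE of the group-by-time term.

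| Scenario | No strata | Main effects | Plus time interactions |
|---|---|---|---|
| Level gaps 10 and 5 | 1.568 | 1.566 | 1.566 |
| Change gaps 5 and 5 | 1.576 | 1.576 | 1.553 |
| Level gaps 10 and 5, change gaps 10 and 5 | 1.633 | 1.631 | 1.567 |

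Main effects do almost nothing; the time interactions recover the precision. The relative excess is 1.576/1.553 − 1 = 1.5% and 1.633/1.567 − 1 = 4.2%, close to step 4.

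**The case against.** The strongest reply is that the primary effect is a within-person contrast. Different staff, patient pools or monitors at the two sites mainly shift BP level, and a shift that is the same at both visits drops out. The Protocol (Informed Consent Procedures) also has one project manager train both sites' assistants weekly, and nothing in either document gives or implies a site or sex difference in BP change. This stands. It limits the point to differences in change, whose size is unknown. A 10 mm Hg gap in change between sites would be twice the effect that the trial is designed to detect, so the 5 mm Hg rows are the fairer guide.

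It can also be said that a multilevel model with a general random-effects term leaves room for site. But the SAP names only the person level, and a site intercept would absorb level, not change.

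A reader might infer that any site difference inflates the error, or that the benefit of stratifying is lost. The documents do not support either reading. Level differences cancel, and the estimate keeps the lower true variance that stratification gives; only the reported error is conservative. Nor does the omission produce bias, extra false positives or a shortfall against the stated power.

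**Conclusion.** The specification gap is real and minor. The strata used in allocation are absent from the primary model, and no rule in the SAP would bring them in. If stratum differences in change are of the order of 5 mm Hg, the primary standard error is overstated by 1 to 2%; at 10 mm Hg between sites the figure is about 4%. Power remains about 86% or more in every case tabulated. These sizes rest on assumed differences, 1:1 allocation, equal sites, 20% women and dropout at random. Fewer women would shrink the sex contribution. No separate calculation was made for the Hypothesis 2 scales; the recommendation extends to them because the SAP has them follow the Hypothesis 1 analysis.

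**What to change.** State in the SAP that the primary Hypothesis 1 model, and the Hypothesis 2 models that mirror it, include site and sex as fixed effects together with site-by-time and sex-by-time terms. A change-score model with site and sex as covariates would serve the same purpose. Main effects alone should not be accepted as sufficient. Keep the imbalance rule for other covariates, in secondary analyses. The cost is one sentence and a few degrees of freedom out of about 510, with no new data.

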Secondary Analyses: Covariates to account for substantial imbalances in group characteristics will be added to our main regression models. Secondary analysis will occur for the separate measures of HTN management behaviors and BP change. As in our prior trials, we will also conduct secondary stratified analyses above and below the median mean arterial pressure at baseline (in our prior VA stories, we found the effect greater in those below the median baseline BP (see Section B5.b)). We will also analyze effect by site, by chosen storyteller and by age group. Further, using the administrative data for MPR, we have a pragmatic opportunity to study sustainment of effect after the six-month CTC is completed. For the subset of patients with six-months completed before Year 4, we will also calculate MPR six months after the end of CTC. In a secondary model, three time periods (before, during, after CTC) will be jointly tested using "segmented regression" to account for the three time periods.

Hypothesis 3: The effect of CTC on BP will be mediated by the more proximal measures of (H3a) cognitive and emotional processes (i.e.: emotional engagement with stories, self-efficacy), and (H3b) HTN management behaviors.

For this hypothesis, we will conduct a formal mediation analysis. Initial methods will follow Barron and Kenny's

protocols, with more recent advances developed by MacKinnon. Mediation occurs when an intervention changes the rate of uptake of an intermediate process that directly influences outcome. Mediation analysis can help to disentangle the mechanisms which may contribute to intervention effectiveness. We will estimate the proportion of the intervention effect that is transmitted through each of these mediators and quantify the precision of these estimates with 95% bias-corrected and accelerated bootstrap confidence intervals. Thus, we will be able to quantify the relative proportional mediation for each of the measures listed in Hypothesis 2.

Power Calculations

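### Whether the effect varies with baseline BP is examined only by separate analyses either side of median MAP, with no test or confidence interval for the difference

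*SAP*

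**What the plan says.** The Secondary Analyses paragraph of the SAP's Analysis Plan states that, as in the group's earlier trials, "we will also conduct secondary stratified analyses above and below the median mean arterial pressure at baseline". In parentheses it adds that in the prior VA trial "we found the effect greater in those below the median baseline BP", pointing to a section that is not part of the supplied documents.

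Nothing further is said about how the two halves will be compared. The only interaction specified for blood pressure is group by time, under Hypothesis 1, and that term is the treatment effect itself. No group-by-time-by-MAP term, interval for the between-half difference, or rule for reading unlike results appears in the SAP or the protocol. The general rule is "All analyses will be two-sided, with alpha error = 0.05", with no separate provision for subgroups.

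**The concern.** Saying that an effect is greater in one half than in the other is a statement about a difference between two effects. Two separate analyses do not estimate that difference or give its uncertainty. Each half holds about half the participants, so each has much less power than the whole trial. With one common true effect, it is then quite likely that one half crosses 0.05 and the other does not.

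At stake is the reading of a result that the investigators already carry forward from their prior trial. If this trial shows significance only below the median, it may look like replication; if only above, like a reversal. Either pattern can easily arise by chance, and either could influence whom the intervention is offered to.

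**Working it through.** **Inputs.** From the SAP's Power Calculations: N = 600, follow-up 85% (82% as the lower scenario), within-person correlation 0.5, SD 18 mm Hg, target difference 5 mm Hg. The prior effects are also there: "Difference in BP for our video stories alone ranged up to 6mm Hg, and as low as 2.7mm Hg". Alpha is two-sided 0.05. The allocation ratio is not stated; 1:1 is assumed, with equal follow-up in the two halves.

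**Reproducing the SAP's figure.**
- SD of change = 18 × √(2 × (1 − 0.5)) = 18.
- At 85% follow-up there are 510 participants, 255 per arm. SE = 18 × √(2/255) = 1.59, so power at 5 mm Hg is 88.0%.
- At 82% follow-up, 246 per arm, power is 86.9%.

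Both agree with the claim of over 80%.

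**Within each half.** About 255/2 = 127.5 per arm.
- SE = 18 × √(2/127.5) = 2.25 mm Hg. Power at 5 mm Hg = 60.2%.
- If the split is made on a variable perfectly correlated with the analysed BP, baseline variance within a half shrinks by the half-normal factor 0.363. Change variance = 0.25 × 324 × 0.363 + 243 = 272, so SD = 16.5, SE = 2.07 and power = 67.7%. This is the extreme case; MAP would lie somewhere between the two.

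**Chance of exactly one significant half when the true effect is equal in both**, 2p(1 − p), at 85% follow-up:

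| True effect in both halves | SD of change 18 | SD of change 16.5 |
|---|---|---|
| 5 mm Hg | 47.9% | 43.8% |
| 2.7 mm Hg | about 35% | about 38% |
| 6 mm Hg | 36.6% | 28.6% |
| none | 9.5% | 9.5% |

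At 82% follow-up and SD 18, the 5 mm Hg figure is 48.5%. Simulation of 510 followed participants, split on a variable correlated 0.8 or 1.0 with baseline systolic BP, gave 43–46% at 5 mm Hg and 37–40% at 2.7 mm Hg. Restricting to simulated trials with a significant overall result at 5 mm Hg does not remove the problem: 43–48% of those still had one half significant and the other not.

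These figures count both directions. With equal power in the two halves, each direction takes half: at 5 mm Hg, about 22–24% significant only below the median and 22–24% only above.

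**The direct comparison of halves.**
- SE of the difference = √2 × 2.25 = 3.19 mm Hg (2.92 with SD 16.5).
- False-positive rate when the effects are equal: 5% by construction, 4.8–5.4% in simulation.
- With equal true effects, the two estimates differ by more than 5 mm Hg in about 12% of trials (9% with SD 16.5).
- Power for a true 5 mm Hg difference between halves: 35% (40% with SD 16.5).
- Difference detectable with 80% power: 2.80 × 3.19 = 8.9 mm Hg (8.2 with SD 16.5).

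**Continuous MAP.** If MAP is normally distributed and the effect changes linearly with it, a median cut keeps 2/π = 64% of the efficiency. For the same 5 mm Hg between-half difference with SD 18, the expected test ratio rises from 5/3.19 = 1.57 to 1.57 × √(π/2) = 1.97, which is about 50% power. That is better, but still low.

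**The case against.** The strongest reply is that the SAP never says effect modification will be judged by which half is significant. It plans stratified analyses, calls them secondary, and gives continuity with earlier trials as the reason; two estimates with intervals can be shown descriptively. That stands. A reader might infer that 44–48% is the error rate of the planned analysis. It is not: it is the chance of discordant significance at one assumed effect, near where discordance peaks, and it misleads only someone who reads discordance as a difference. The documents neither state nor exclude that reading.

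A reader might also infer that testing the prior trial's finding is the declared purpose. The SAP mentions that finding only in parentheses and sets no such aim.

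A third tempting inference is that splitting on baseline BP, itself one of the two repeated outcomes, biases the comparison by truncating it. The documents do not support this. MAP at baseline precedes treatment, and regression to the mean acts equally in both arms, so the between-arm contrast within a half is not biased by the split. The narrower SD even raises within-half power slightly.

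Finally, an interaction test is itself weak here, and a non-significant result would say little. That is true. It argues for reporting the interval and calling the analysis exploratory; two separate p-values would hide the same imprecision.

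**Conclusion.** The concern holds in a limited form. The SAP's only look at variation of effect with baseline BP is a pair of separate analyses, with no test or interval for their difference. Under its own inputs, a common true effect would make exactly one half significant in roughly 44–48% of trials at the design effect and 29–38% at the ends of the prior range, against about 5% false positives for an interaction test. With no treatment effect the discordance is 9.5%, so the risk is greatest when the intervention works.

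The figures rest on 1:1 allocation, equal follow-up in both halves, a normal approximation, and a within-half SD of change between 16.5 and 18 mm Hg. A reader might take this as a doubt about the primary result; it is not, since Hypothesis 1, its model and its power are untouched. The change should be made because it is cheap and the subgroup claim is already in circulation, but it concerns a secondary analysis.

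**What to change.** Make the effect-modification analysis an interaction with baseline MAP as a continuous variable, in one of two forms chosen in advance:

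- arm by time by MAP, with all lower-order terms, in the SAP's repeated-measures model; or
- arm by MAP, with both main effects, in a model of 6-month BP.

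Report the estimate with its 95% CI and label the analysis exploratory. State the low power: about 35–40% for a 5 mm Hg difference between halves, with a detectable difference of about 8–9 mm Hg. Keep the above- and below-median results as a descriptive display for comparison with the prior trial, and say that significance in one half and not the other will not be read as evidence of a difference.

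The cost is SAP wording and one further model; no new data are needed. The first form needs several added terms. The second leaves out participants who have no 6-month value, so the SAP's commitment to use all available data should be addressed if it is chosen. An interaction slope is also harder to present than two subgroup estimates, which is why the descriptive display is worth keeping.
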